8.4.1.3 VISIT 3 (Open Challenge to CM Formula)

Visit 3 will take place min:2 days, max:4 weeks after visit 2. Participants will be monitored by a delegated clinician, supported by a delegated nurse(s) and will remain in the department for up to 8 hours, as appropriate. In rare cases and if they experience severe anaphylaxis, they may need to be hospitalised overnight, as per the clinical judgment of the clinician.

Participants will undergo the following assessments:

- 1. Physical Examination, current medical history & vital signs: Weight, length, EASI Score & history of wheeze. The following will be confirmed to be normal and a statement to this effect recorded in the medical notes: General physical examination with chest auscultation, Peripheral arterial pulse, heart rate, systolic and diastolic blood pressure, respiratory rate, and oxygen saturation.
- 2. Collect stool samples: These will be collected only where **consent** has been provided and stored locally until transferred to the central laboratory.
- 3. Open challenge to CM Formula: as per the trial SOPs. Results of the challenge must be recorded in the **participant's medical notes**.
- Reassessment and confirmation of eligibility: A medically qualified doctor authorised on the site Delegation of Authority and Signature Log must confirm full eligibility of the patient (see section 6). A record of this confirmation must be made in the patient's medical notes and appropriate CRF.

In the event of weight loss during the trial screening period, randomisation may be postponed until the required weight is achieved, providing all other inclusion criteria are met and visits fall within the required timeframes.

- 5. Allocation to a randomised treatment (if meeting criteria as follows) see section 8.5 for randomisation procedures:
 - Participants with a *negative* result at this challenge will not be randomised; they will not proceed any further in the trial.
 - Participants with a *positive* result at this challenge will be randomised *and* will skip visits 4, 5 and 6, *and* will proceed directly to VISIT 7 (Mid Trial Visit).

- 6. Prescribe adequate amount of allocated study product for home: Complete study prescription for the pharmacy/unblinded team to dispense the allocated study product to **randomised participants**. An adequate number of tins should be prescribed to supply the participant with enough formula to last until further product is received at home. Pharmacy/unblinded team will also complete appropriate accountability logs and the Sharp product request form to request further product for home delivery using the appropriate request form.
- 7. Providing diary and instructions for use: Give *randomised participants* diaries and instructions for filling in.
- 8. Provide stool sample containers for the next visit: Provide eligible participants with containers for the collection of stool samples at home. Parents should take samples as close to visit 7 as possible, and only from participants whose parents have provided **consent** for these additional samplings.
- 9. Follow up communication: A follow-up communication (phone/email) will take place for all challenge participants regardless of whether they were randomised within 48 hours. Any late symptoms should be recorded in the **participant's medical notes**, and the clinician should assess if they are possibly associated with the challenge and record this in the participant's medical notes and transcribed onto the CRFs.

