3.4.2 Secondary Outcomes/Endpoints

- 1. The dose at which reactivity occurs in the DBPCFC
- 2. The maximal wheal size of skin prick test to cows' milk
- 3. Specific IgE levels to cows' milk, casein, a-lactalbumin and b-lactoglobulin
- 4. EASI scores for Eczema
- 5. Wheeze (during last 12 months, use of systemic steroids, hospitalisations)
- 6. Doctor diagnosis of other food allergies
- 7. Height
- 8. Weight
- 9. Adverse events from the visit where infants are put on the study product (V3 for 'pHF tolerant' and V4 for 'pHF-reactive' CMA infants) to the final visit (V9)

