7 PARTICIPANT TIMELINE, ASSESSMENTS AND PROCEDURES

	V ₁	V ₂	V ₃	V_4	V 5	V ₆	TC1	V ₇	TC2	V ₈	V۹
	Screening visit	phf challenge	CM challenge ¹	1 st OIT Visit ²	2 nd OIT Visit ²	3 rd OIT Visit ²	Telephone call 1 ¹	Mid-study assessment	Telephone call 2 ³	1 st part DBPCFC to CM	2 nd part DBPCFC to CM
ACTIVITY		3-21 Ds from V1	2-28 Ds from V2	2-6 Ws from V2	4-6 Ws from Randomisation (V4) ⁴	8-12 Ws from Randomisation (V4) ⁴	12 Ws (+/- 2) from Randomisation (V3)	24 Ws (+/- 2) from Randomisation (V3 or V4)	36 Ws (+/- 2) from Randomisation (V3 or V4)	48 Ws (+/- 2) from Randomisation (V3 or V4)	1-4 Ws from V8
Informed consent signed	X										
Assessment of eligibility	х	х	x								
Confirmation of eligibility			x	х							
Demographics & review of medical history and diet ⁵	X										x
Assessment of Adverse events				Х	x	х	х	х	х	х	х
Physical Examination, current medical history & vital signs ⁶	X	x	x	X	х	X		х		x	x
Skin Prick Testing ⁷	Х									х	
Blood samples for antigen specific IgE ⁸	X									x	
Blood samples for safety markers ⁹	X										
Blood samples for storing ¹⁰	X							х		х	
Buccal samples for storing ¹¹		х						х		х	
Provide stool sample containers		x	(x)			Х		х			
Collection of stool samples for storing ¹²			х	Х				х		х	
Randomisation ¹³			(x)	х							
Dispensing of randomised			(x)	Х	х	х					
study product for home ¹⁴ Provide diary and instructions								v		v	
			(x)	X	X	X		X		X	
Collect and review Diary					X	X		X		X	X
Oral Immunotherapy (OIT)				X	X	X					
Oral Challenge and follow-up call		X	X							X	X
Telephone questions ¹⁵							х		х		

¹ Only applicable to participants with a negative reaction to pHF at V2.

² Only applicable to participants with a positive reaction to pHF V2.

³Telephone call 2 will take place for all participants 36 weeks (+/- 2w) after randomisation.

⁴ There must be at least 4 weeks between each of the OIT visits (V4, V5 and V6).

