8.7.1.1 VISIT 4 (OIT Visit 1)

Visit 4 will be conducted 2-6 weeks after visit 2 (these participants skipped visit 3) and will take up to 8 hours.

Participants will undergo the following assessments:

- 1. Confirm eligibility to continue participation.
- 2. Allocation to randomised treatment: Participants attending visit 4 (these are the participants with a positive result to VISIT 2 (Open Challenge to pHF) will be randomised (see section 8.5).
- 3. Collect stool samples: These will be collected only where **consent** has been provided and stored locally until transferred to the central laboratory.
- 4. Physical Examination, current medical history & vital signs to be assessed prior to OIT schedule: Weight, length, EASI Score & history of wheeze. The following will be confirmed to be normal and a statement to this effect recorded in the medical notes: General physical examination with chest auscultation, Peripheral arterial pulse, heart rate, systolic and diastolic blood pressure, respiratory rate, and oxygen saturation.
- 5. OIT dose escalation schedule: will be conducted as per the trial OIT SOPs. Results of the OIT must be recorded in the **participant's medical notes**.
- 6. Prescribe allocated study product for home: Complete study prescription for the pharmacy/unblinded team to dispense an adequate amount of the allocated study product. An adequate number of tins should be prescribed to supply the participant with enough formula to last until the next visit (or until further product is received at home if no further OIT visits are required). Pharmacy/unblinded team will complete appropriate accountability logs and, if necessary, the Sharp product request form to request further product for home delivery using the appropriate request form.
- 7. Provide diary and instructions for use: Give participants diary and instructions for filling in.
- 8. Record AEs: Any AEs occurring from this visit must be recorded in the participant's medical notes and on the AE Log (see section 10).

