9 TRIAL TREATMENT/INTERVENTIONS

9.1 Introduction

This study will randomise the participants in 2 groups.

- The first group is normal care and will receive an approved, already in the market eHF formula which has the indication to be used for milk-allergic infants, such as those participating in the study. There is already significant experience with this formula and is nutritionally complete and widely used for this indication. The management of the infants of this arm in regard to the formula will not differ from routine care.
- The other arm will receive a market-approved, already in the market pHF formula which has the indication to be used for infants with colic and for allergy prevention. There is already significant experience with this formula and is nutritionally complete and widely used for this indication. This formula does not have an indication to be used for milk allergic infants.

Neither of these formulas is an investigational medicinal product and MHRA has confirmed that no Clinical Trial Authorisation (CTA) is needed for this trial (see APPENDICES 1).

The main intervention consists of free feeding with pHF as compared to the standard care of free feeding with eHF. Infants who can already tolerate pHF will start free feeding with pHF or eHF from visit 3 onwards. Those who react initially to pHF (visit 2) will undergo a short OIT module to either pHF or eHF (see Schematic of Trial Design).

The pHF free feeding intervention.

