10 SAFETY REPORTING

10.1 Time Period for Active Monitoring of Safety Events

The "active monitoring" of all safety events experienced by trial participants will be from randomisation until 48 hours after visit 9.

Any additional information on selected adverse events related to the initial challenges, will be captured in the Challenge Form (see sections 8.4.1.2 and 8.4.1.3). Expected adverse events during the challenges will not be included in the adverse events log, but rather in the challenge logs.

Any safety events occurring *after* the end the active monitoring period that meet the definition of **serious** (see section 10.3) must continue to be reported by sites to the LCTC in accordance with the timeframes and procedures described in section 10.9.

Upon becoming aware of a serious adverse event (SAE/Related SAE/RUSAE), the investigator or other delegated member of the site team must report this to the LCTC **within 24 hours**.

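### Adverse event collection starts at V3 for pHF-tolerant infants, but V3 has no adverse event step and its 48-hour contact attributes symptoms only to the challenge

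*Protocol*

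**What the plan says.** **Start of collection.** Secondary outcome 9 (Protocol 3.4.2) is "Adverse events from the visit where infants are put on the study product", which it gives as V3 for pHF-tolerant infants and V4 for pHF-reactive infants. Section 10.1 says active monitoring "will be from randomisation until 48 hours after visit 9". For pHF-tolerant infants, randomisation is at V3.

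**Start of study product.** Section 9.1 says: "Infants who can already tolerate pHF will start free feeding with pHF or eHF from visit 3 onwards". Section 8.4.1.3 has the formula dispensed at V3, and 9.2.3 has free feeding brought in gradually over the following week.

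**Visit instructions.** In the Section 7 schedule, the row "Assessment of Adverse events" has no mark at V1, V2 or V3. Its first mark is at V4. The V4 list (8.7.1.1, item 8) includes a recording step: "Any AEs occurring from this visit must be recorded". The lists for V5 to V9 have one too; the V3 list does not.

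**The 48-hour contact after V3** (8.4.1.3, item 9). Late symptoms of any kind go into the medical notes and on to the CRFs, and "the clinician should assess if they are possibly associated with the challenge". The item mentions neither the study formula nor the AE log.

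**Challenge events.** Section 10.1 has information on selected events related to the initial challenges captured on the Challenge Form, and points to 8.4.1.3 for this. It adds: "Expected adverse events during the challenges will not be included in the adverse events log, but rather in the challenge logs".

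**The concern.** The definition of the outcome and the instructions to sites disagree at the moment a pHF-tolerant infant first receives study product. A site that follows the schedule and the V3 list has no prompt to open an AE record. The one contact soon afterwards directs the clinician's judgement to the challenge alone.

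The likely error also has a direction. Section 9.1 describes pHF as about 60 times less allergenic than cow's milk and eHF as 20 million times less allergenic, so reactions to the first feeds are expected mainly on pHF. Filing such a reaction as a late challenge symptom would make pHF look safer. Section 3.3 states the hypothesis that pHF is as safe as eHF, and 11.5 presents related AEs and SAEs by treatment group, so both attribution and the form used affect what is reported.

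**Working it through.** The protocol states no figure on this point. The check sets its sections side by side and then works out timing and scale.

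**1. The two randomisation visits compared**

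| | V3 (pHF-tolerant) | V4 (pHF-reactive) |
|---|---|---|
| Outcome 9 starts here | yes | yes |
| Randomisation, dispensing, diary | yes, marked (x) in Section 7 | yes |
| Mark in the AE row | none | yes |
| AE-recording step in visit list | none | item 8 |
| Next scheduled AE assessment | telephone call 1 | V5 |

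Section 7 already uses the conditional mark (x) at V3 for randomisation, dispensing and diary. The blank in the AE row therefore looks like an oversight.

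**2. The 48-hour contact**

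The V2 follow-up (8.4.1.2) has the same attribution question. At V2 it fits, because no study formula has been given. At V3 the infant may have had two relevant exposures within 48 hours: the cow's milk challenge, and the first feeds at home. The question still covers only the first. The expected events in Table 4 include anaphylaxis, urticaria and allergic reaction, which either exposure could produce.

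**3. Timing from the stated windows**

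- Telephone call 1: 12 ± 2 weeks = 10–14 weeks after randomisation.
- V7, the first diary review for these infants: 24 ± 2 weeks = 22–26 weeks.
- For pHF-reactive infants: V4 on the day of randomisation, then V5 at 4–6 weeks.

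**4. Scale, from the assumptions in 11.3.1**

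- Proportion reacting to pHF at V2: 0.33.
- Proportion tolerating pHF but reacting to cow's milk at V3: 0.67 × 0.50 = 0.335.
- Share of randomised infants on the V3 route: 0.335 / (0.33 + 0.335) = 0.335 / 0.665 = 50.4%.
- Number: 206 × 0.504 ≈ 104, about 52 of them on pHF.
- With 90% cow's milk reactivity, since 11.3.1 describes reactivity as over 90%: 0.67 × 0.90 = 0.603; 0.603 / 0.933 = 64.6%; 206 × 0.646 ≈ 133.

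These are the numbers of infants following the route. They do not estimate how many events would be misfiled or captured late.

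**The case against.** The strongest reply is that the protocol already obliges sites to capture these events.

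- Item 9 records any late symptoms. Only the causality judgement is tied to the challenge.
- The AE-log exclusion in 10.1 covers expected events during the challenges, and a reaction to a home feed is not one.
- Sections 10.9.2 and 10.11 require every safety event on an AE form, whether or not related or expected, and sent within 7 days of the site learning of it.
- Parents receive a diary at V3. V7 reviews it and moves new AEs to the AE log. Telephone call 1 asks about any adverse events.

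All of this stands. A reader might infer that the 48-hour contact asks only about the challenge, that early reactions are lost altogether, or that they rest on parental recall alone. The documents support none of these.

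It can also be said that misfiling is unlikely. It needs a feed within 48 hours, a reaction, and attribution to the wrong exposure. Section 9.2.3 indicates that most reactions may come within about an hour of feeding, so timing would often separate the two exposures. These infants have also passed a pHF challenge at V2. This bears on how many events are at risk and supports a small number.

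The Open Challenge SOP is not shown and may say more about late symptoms. Even so, the conflict between 3.4.2, 10.1, Section 7 and 8.4.1.3 lies within the protocol itself.

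The general duty does not fully answer the point. It takes effect once the site is aware of an event, and the contact most likely to make it aware steers attribution to the challenge, whose related events 10.1 directs to the Challenge Form.

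**Conclusion.** The inconsistency holds: AE collection is defined from V3 for pHF-tolerant infants, while the schedule and the V3 list contain no AE step and the early contact asks for attribution to the challenge only. The supported consequence is possible misattribution of early formula reactions, or late prompting at 10–14 weeks (telephone call 1) and 22–26 weeks (V7 diary review).

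About 104 of 206 infants take this route if 50% of those tolerating pHF react to cow's milk, and about 133 if 90% do. The number of events affected cannot be derived from the protocol and is probably small. The direction, in favour of pHF, rests on the protocol's own account of relative allergenicity. Section 11.5 plans no formal safety comparison, so a descriptive table is at stake and no test result. The change is still worth making, because it alters what sites do when study product starts and aligns the two randomisation visits.

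**What to change.** 1. In Section 7, mark V3 as (x) in the AE row, for randomised infants.
2. Add V4's AE-recording step to 8.4.1.3, to apply after randomisation.
3. In 8.4.1.3 item 9, state for randomised infants that the contact asks whether study formula has been started, that symptoms beginning after randomisation go on the AE form, and that relation to the challenge and relation to the study formula are recorded separately.
4. Add a cross-reference in 10.1, so that its Challenge Form wording is not read as covering symptoms that begin after randomisation.

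The cost is one schedule mark, one visit step, one question in a contact that already takes place, and a line in 10.1. The small downside is that some late challenge symptoms will also appear on the AE form, with their cause marked.

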8.5 Randomisation Procedures

Participants will be randomised to receive either normal care (eHF) or the intervention (pHF) in a 1:1 ratio once:

- a. Fully informed written consent/proxy consent has been obtained.
- b. Eligibility criteria have been fulfilled as confirmed by a medically qualified doctor.
- c. Baseline assessments have been completed.

Participants will be randomised at visit 3 or 4 using a secure (24-hour) web-based randomisation programme controlled centrally by the LCTC. A personal login username and password, provided by the LCTC, will be required to access the randomisation system; designated research staff will be issued with their personal login and password upon completion of training in the use of the system.

When the system requirements (consent, eligibility and baseline assessments at visits 1, 2 and 3) are confirmed, a unique study number (randomisation number) will be displayed on a secure webpage and an automated email confirmation will be sent to the authorised randomiser, PI and Trial Manager – this will not contain the treatment allocation. A separate email containing the treatment allocation will be sent to members of the pharmacy department or appropriate unblinded staff members responsible for dispensing the study formula, and Sharp. It is the responsibility of the PI or delegated research staff to inform the pharmacy department at their centre prior to randomisation to ensure there is sufficient supply of the study treatments.

Randomisation: web access https://ctrc.liv.ac.uk/Randomisation/DREAM

If there are any problems with the randomisation systems contact the LCTC on [name] or via email on [contact]

(Note that the LCTC is open from 0900 – 1700, Monday – Friday, excluding public holidays and University of Liverpool closure days.)

In the event of a randomisation system failure, the centre should contact the coordinating team in CTU (Monday to Friday between 9:00 to 17:00 excluding bank holidays and University of Liverpool closure days) to try to resolve the problem. If the problem cannot be resolved the coordinating CTU will perform central randomisation and randomise the participant using the back-up randomisation system. The back-up randomisation system is an exact replica of the live system but is based on a standalone PC at CTU.

8.6 Who is Blinded to Allocations

Parents of participants, LCTC staff (excluding statistical team members as appropriate) and all members of the site research teams managing trial participants will be blinded to treatment allocations.

Nutricia will provide matched pHF and eHF tins with blinded labelling. The formulas themselves will not be processed for blinding and will be altered in no way from the original market-approved products. This means that the products will not be exactly identical, but they are similar and it is expected that unless the parents actively go to great lengths to break the blind, the blinding will be preserved.

Nutricia will also label tins with unique tin numbers. When Nutricia send tins to Sharp, they will also provide a tin allocation list detailing which tins are eHF and which are pHF. The unblinded statistician at LCTC will also receive this list.

When Sharp send tins to pharmacies or appropriate unblinded staff, they will also provide a tin allocation list detailing which of the received tins are eHF and which are pHF.

When pharmacy or unblinded staff dispense initial tins to participants, they will record which tin numbers have been dispensed. Similarly, when Sharp send additional tins to participants, they will record which tin numbers have been provided.

8.7 Schedule for Follow-up

8.7.1 Oral ImmunoTherapy (OIT) Visits

Participants will undergo several increasing doses of their allocated formula during each OIT visit. Please see study OIT SOP.

8.7.1.1 VISIT 4 (OIT Visit 1)

Visit 4 will be conducted 2-6 weeks after visit 2 (these participants skipped visit 3) and will take up to 8 hours.

Participants will undergo the following assessments:

- 1. Confirm eligibility to continue participation.
- 2. Allocation to randomised treatment: Participants attending visit 4 (these are the participants with a positive result to VISIT 2 (Open Challenge to pHF) will be randomised (see section 8.5).
- 3. Collect stool samples: These will be collected only where **consent** has been provided and stored locally until transferred to the central laboratory.
- 4. Physical Examination, current medical history & vital signs to be assessed prior to OIT schedule: Weight, length, EASI Score & history of wheeze. The following will be confirmed to be normal and a statement to this effect recorded in the medical notes: General physical examination with chest auscultation, Peripheral arterial pulse, heart rate, systolic and diastolic blood pressure, respiratory rate, and oxygen saturation.
- 5. OIT dose escalation schedule: will be conducted as per the trial OIT SOPs. Results of the OIT must be recorded in the **participant's medical notes**.
- 6. Prescribe allocated study product for home: Complete study prescription for the pharmacy/unblinded team to dispense an adequate amount of the allocated study product. An adequate number of tins should be prescribed to supply the participant with enough formula to last until the next visit (or until further product is received at home if no further OIT visits are required). Pharmacy/unblinded team will complete appropriate accountability logs and, if necessary, the Sharp product request form to request further product for home delivery using the appropriate request form.
- 7. Provide diary and instructions for use: Give participants diary and instructions for filling in.
- 8. Record AEs: Any AEs occurring from this visit must be recorded in the participant's medical notes and on the AE Log (see section 10).

